Corrections made on pages 23, 24 and 26 are to clarify that the primary outcome of change in pain scores is not from ED arrival to discharge, but from the time of placement in a treatment area to the time of disposition (hospital admission, discharged home, assigned to observation status) or a maximum treatment duration of 6 hours, whichever comes first.

[figure not shown]
Section 13.9

Correction made on page 26 is to clarify that the secondary outcome of ED length of stay is from ED arrival to discharge.

1. EXECUTIVE SUMMARY

Title:	A Comparison of Individualized vs. Weight Based Protocols To Treat Vaso-Oclusive Episodes in Sickle Cell Disease (COMPARE VOE)
Location:	6 clinical sites (Emergency Departments) in the United States
Objectives:	To compare the two analgesic protocols recommended by the NHLBI for treating VOE in the Emergency Department.
Study Design:	A Phase III single-blinded randomized study of approximately 460 participants to capture data on 230 participants with one ED visit in the study population.
Treatment Regimens:	1:1 treatment allocation will be used with site as the stratification variable. Subjects will be randomized to receive analgesic management for VOE either via a weight-based SCD analgesic, or a patient-specific analgesic developed by their primary SCD outpatient provider.
Primary Endpoint:	Change in pain scores in the ED from the time of placement in treatment area to the time of disposition (hospital admission, discharged home or assigned to observation status) or a maximum treatment duration of 6 hours, whichever comes first
Secondary Endpoints:	
ED length of stayHospitalization for pain controlReturn ED visits, hospitalizations, or day hospital visits within seven days of index ED visit

Study Flow Chart

2. HYPOTHESES AND OBJECTIVES

2.1 Primary Objectives and Hypothesis

The primary objective of the COMPARE-VOE study is to compare change in pain scores in response to two different treatment regimens for treating acute painful VOE in SCD. All patients will be followed for a maximum of 6 hours in the ED, or until time of placement in observation status, discharge or inpatient admission.

Our **primary hypothesis** is that the patient-specific analgesic protocol is superior to the weight-based analgesic protocol. A sample size of 230 subjects with ED visits provides 90% power to detect a 14-mm clinically significant reduction in pain scores between the two groups with 0.05 type I error using a horizontal Visual Analogue Scale 100 mm in length. This assumes the same standard deviation (SD) of 31 mm in pain score reductions in the two groups while accounting for 10% missing data rate.

2.2 Secondary Objectives

The secondary objectives of this study protocol will be the following endpoints:

- ED length of stay
- Hospitalization for pain control
- Return ED visits, hospitalizations or day hospital visits within seven days of the index ED visit

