8.2. Randomization and Patient Analgesic Protocols

After patients have provided informed written consent, they will be randomized to either

the weight-based analgesic protocol or a patient-specific analgesic protocol that will be developed by their hematologist/sickle cell team. A 1:1 treatment allocation will be used with site as the stratification variable. A computer-generated permuted block randomization schedule with stratification by clinical site will be prepared by the DCC senior statistician with block size randomly chosen that will not be revealed to investigators. This scheme provides chronological balance during enrollment with respect to the number of patients allocated to each treatment arm, and thus balances the treatment groups with respect to possible changes in the mix of patients over time. For the sites, the randomization will be available through the password protected and customized web-based electronic data capture (EDC) system. The EDC will be maintained by the DCC data management team. Treatment plans can be updated as needed by the hematologist.

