13. STATISTICAL CONSIDERATIONS

13.6. Overview

Detailed description of the plan for statistical analysis of each endpoint will be detailed in a Statistical Analysis Plan (SAP) that will be prepared after the final study protocol is approved. The SAP will be prepared by the DCC senior statistician under [name] supervision.

Descriptive statistics will be used to summarize patient socio-demographic and clinical characteristics. The analyses of primary and secondary outcomes as well as the summary description of pain-related side effects and safety will be carried out by the DCC statistical service. Means, standard deviations, medians, 25th and 75th percentiles, minimum and maximum will be presented for continuous variables; the number and frequency of patients in each category will be presented for nominal variables. For all analyses, a two-sided p-value ≤ 0.05 will be considered statistically significant. Analyses will be performed using SAS version 9.4 or higher software (SAS Institute, Inc., Cary, NC).

Multiple Comparisons: With the pre-specified primary and secondary analyses, we

recognize that there is a multiplicity of analyses to be performed, which leads to an increased probability that at least one of the comparisons could be "significant" by chance. There are adjustments (e.g., based on the Bonferroni inequality) that can be used to preserve the overall type I error level. To attempt to adjust for the effects of the repeated significance testing that will occur as part of potential interim monitoring (discussed below), plus to adjust for the multiplicity of secondary outcomes, would require that very small significance levels be used for every comparison. Rather than taking this approach we will be conservative in the interpretation of secondary analyses, taking into account the degree of significance, and looking for consistency across outcomes. The actual p-value for each comparison will be reported to aid in the overall interpretation. In addition to the pre-specified primary outcome, we will use pre-specified secondary outcomes and pre-specified subgroups to help avoid over-interpretation and to help guard against and reduce the problems inherent with multiple testing.

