Power calculation for the secondary outcomes are performed for the target sample size of 230 at 0.05 level. We do not expect any missing data in the secondary outcomes, as seen in the R34 study. For the length of ED stay from arrival to discharge, we have 83% power to detect a 30-minute difference in length of ED stay between the two analgesic protocols, assuming SD of 78. In the R34 study restricting to the first ED visit, the mean (SD) length time from arrival to discharge was 278 minutes (SD=78). For the secondary outcome of (yes/no) hospital admission in the 1st ED visit, returned ED visit or hospital admission within 7 days of the 1st ED visit, we use 15% as clinical significant difference. We have 64%, 78% and 94% power to detect a 15% difference in hospitalization rates in the 1st ED visit, in rates of returned ED visits within 7 days, and in rates of hospital admission within 7

days, respectively, with 0.05 type I error. We have assumed that hospitalization rates are 35% and 50%, the 7-day returned ED rates are 30% and 15%, and 7-day hospitalization rates are 20% and 5%, in the patient-specific and weight-based analgesic protocols, respectively. The assumptions on the hospitalization rates and the return ED visit rates are based on the observations in the R34 study.

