13.9. Analysis of Secondary Outcomes

Analysis of secondary outcomes will be carried out as follows. For the ED length of stay from ED arrival to discharge, a linear regression analysis similar to the primary outcome will be used to compare the length of stay between the two arms. For the hospital admission rate, chi-square test will be used to compare the admission rates between the two groups. For the count data (e.g., ED re-visits or hospitalizations for VOE within 7 days after the recorded ED visit), it will be first evaluated by collapsing the data into a binary outcome with a cut off at zero and a chi-square test or Fisher exact test (if frequency is below 5 or less) to compare the re-admission rates or rate of a returned ED visit between the two groups. If there is sufficient spread in the count data, a Poisson regression approach will be used to test for protocol differences in the count outcome.

13.10. Analysis of Exploratory Safety Outcomes:

The frequency with which various side effects, adverse event (AE) or serious adverse events (SAE) occur will be carefully tabulated and descriptively summarized. Statistical comparisons of the randomized arms with respect to these events will use chi-square, Fisher exact or other appropriate two-sample methods depending on the nature of the event, interpreting such comparisons in the context of differences between the two randomized arms in the primary and major secondary outcomes and bringing to bear clinical judgment as to the relative seriousness of these side effects and various adverse events.

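### Index hospitalization and 7-day ED return, the outcomes with the lowest stated power, are tested without the covariates used for the primary endpoint; adjusting would be a cheap but modest efficiency gain

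*Protocol*

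**What the plan says.** Protocol 2.2 names "Hospitalization for pain control" among the secondary endpoints. Protocol 13.9 gives the method: "For the hospital admission rate, chi-square test will be used to compare the admission rates between the two groups". SAP 4.2 repeats that sentence. In both documents the 7-day outcomes are first reduced to none versus any and compared by chi-square, or by Fisher when counts are small. A Poisson model follows if the counts are spread enough, but no covariates are named for it.

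The continuous endpoints are treated differently. Protocol 13.8 and SAP 4.1 and 7.7.1 analyse the primary endpoint by linear regression with adjustment for initial pain, genotype, age and gender. Length of stay gets a regression modelled on the primary one. SAP 6.2 names the same four covariates for Cox models, although no listed endpoint is defined as time-to-event.

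On power, protocol 13.7 states: "We have 64%, 78% and 94% power to detect a 15% difference in hospitalization rates in the 1st ED visit", in 7-day ED return and in 7-day admission, in that order. Primary power is 90% and length-of-stay power 83%.

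SAP Table 17.1 has a column for an estimate with 95% CI in every endpoint row. SAP 4.2 names only tests for the binary rows, and SAP 7.7.2 offers p-values, frequencies and percentages.

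**The concern.** The plan treats four baseline variables as worth adjusting for, then leaves them out for its binary outcomes without giving a reason. Admission for pain control plausibly depends on how bad the pain was at placement, and that score is collected and already sits in the primary model. Index hospitalization (64%) and 7-day ED return (78%) have the two lowest stated powers in the plan, so unused prognostic information costs most there. At stake is some precision on two secondary outcomes, together with an interval estimate that the SAP tables call for but the methods text does not define.

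**Working it through.** **Inputs (protocol 13.6, 13.7, 8.2).** Significance: "a two-sided p-value ≤ 0.05 will be considered statistically significant". Sample size: "Power calculation for the secondary outcomes are performed for the target sample size of 230 at 0.05 level", so 115 per arm under 1:1 allocation. No inflation for missing outcomes: "We do not expect any missing data in the secondary outcomes, as seen in the R34 study". Assumed rates, patient-specific v weight-based: 35% v 50%, 30% v 15%, 20% v 5%.

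**Step 1: reproduce the stated power.** With d = |p1 − p2| and p̄ the mean of the two rates, SE0 = √(2p̄(1−p̄)/115), SE1 = √((p1(1−p1)+p2(1−p2))/115), and power = Φ((d − 1.96·SE0)/SE1).

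| Outcome | SE0 | SE1 | z | Power | Stated |
|---|---|---|---|---|---|
| Index hospitalization | 0.0652 | 0.0644 | 0.345 | 63.5% | 64% |
| 7-day ED return | 0.0551 | 0.0542 | 0.777 | 78.1% | 78% |
| 7-day admission | 0.0436 | 0.0425 | 1.519 | 93.6% | 94% |

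All three match an uncorrected, unadjusted two-proportion test. With a continuity correction they would be 58.3%, 73.1% and 90.6%, which do not match.

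**Step 2: effect of adjustment.** The documents give no prognostic strength. Let R² be the share of outcome variance that the covariates explain (assumed). The effective size per arm is then 115/(1 − R²).

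| R² | Effective n per arm | Index hospitalization | 7-day ED return |
|---|---|---|---|
| 0 | 115 | 63.5% | 78.1% |
| 5% | 121.1 | 65.7% | 80.2% |
| 10% | 127.8 | 68.1% | 82.3% |
| 15% | 135.3 | 70.6% | 84.4% |

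For 7-day admission the rise at 15% is about 3 points.

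**Step 3: simulation check.** This used 4,000 trials per setting and a logistic model with arm and one normal covariate. For hospitalization, chi-square v adjusted power was 65.0% v 66.7% at R² about 0.05, and 65.8% v 70.7% at about 0.12. With a non-prognostic covariate it was 63.8% v 63.1%. The approximation in step 2 holds, and an uninformative covariate brings no gain. The simulation did not fit the full covariate set.

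**Step 4: what adjustment cannot do.** An unadjusted test of hospitalization needs 170 per arm for 80% power. Closing that gap by adjustment alone needs R² = 1 − 115/170, about 32%.

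**Step 5: missing initial pain.** If a complete-case model dropped 10% of patients (the plan's missing rate for the primary endpoint, so an upper figure for initial pain alone), 103.5 per arm would remain. At R² = 10% the effective size is 103.5/0.90 = 115, and the whole gain is lost. Patients with a missing score must therefore be kept.

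**Step 6: events available.** Expected events are 115 × (0.35 + 0.50) ≈ 98 for hospitalization, 115 × (0.30 + 0.15) ≈ 52 for ED return and 115 × (0.20 + 0.05) ≈ 29 for 7-day admission. A model with arm, pain, age, gender, two-group genotype and six sites has 10 terms besides the intercept. That is about 9.8, 5.2 and 2.9 events per term.

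**The case against.** The case against is substantial. A prespecified chi-square test with correctly computed power is a legitimate choice, and protocol 13.6 already commits to cautious reading of secondary results. The covariates may predict little: protocol 13.7 reports that nearly all pilot patients arrived with pain of 67-100 mm and expects high scores again, and a compressed score separates patients less well. The gain could therefore be near zero. A model is also poorly supported for the sparser 7-day outcomes and for the SAP outcomes defined within admitted or non-admitted patients (about 98 and 132 at the assumed rates). All of this stands. It limits the size and scope of the point but does not show that adjustment would do harm.

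Two stronger readings are tempting and not supported.

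- A reader might infer that, because only about half of the randomized patients are analysed, the blocks no longer balance the arms and the admission comparison is distorted. The blocks are stratified by site only ("A 1:1 treatment allocation will be used with site as the stratification variable"). They would not balance initial pain at a future visit even if everyone were analysed, and the test's type I error already covers chance imbalance.
- A reader might infer that every unadjusted outcome is weakly powered. In fact 7-day admission has the highest stated power in the plan (94%), and the 7-day counts may also be modelled by Poisson regression.

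**Conclusion.** The inconsistency is real and appears in both documents, but it concerns efficiency only. The unadjusted tests are valid, and the stated powers are right for the assumed rates. The point applies to index hospitalization and 7-day ED return. If the covariates explain up to 15% of outcome variance, adjustment adds up to about 7 points of power for hospitalization (63.5% to 70.6%) and about 6 for ED return (78.1% to 84.4%). It adds nothing if they are not prognostic. It would not bring hospitalization to 80% unless R² were near 0.32, so the shortfall there comes mainly from sample size and assumed rates, not from the choice of test. The change is worth making because it is cheap and supplies an estimate and interval that SAP Table 17.1 needs.

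**What to change.** Before unblinding, amend protocol 13.9 and SAP 4.2 as follows.

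- For index hospitalization and 7-day ED return, make the main analysis a logistic model with arm, initial pain, genotype (in the two groups the SAP uses for subgroups), age, gender and site. Standardize it to a risk difference with 95% CI by the delta method or bootstrap. Site is the stratification factor, so it belongs in the model even though the primary model omits it.
- Replace a missing initial pain score by the overall mean so that no patient is dropped. SAP 4.1 already uses mean substitution for arrival scores in one sensitivity analysis.
- Keep chi-square or Fisher as supportive for these two outcomes. These results could fill the matching rows of SAP Table 17.2, for which no sensitivity analysis is now defined.
- For the sparser 7-day and subset outcomes, keep chi-square or Fisher as the main analysis, or fix in advance a numeric minimum event count for using the model. Given about 5 events per term at the assumed rates, such a minimum should also cover 7-day ED return.
- State whether the conditional Poisson model carries covariates.

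The cost is SAP wording and a little programming, with no new data or patients. The downside is small: little or no gain if the covariates turn out not to be prognostic.

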3. BACKGROUND AND RATIONALE

Burden of SCD: Sickle cell disease (SCD) is a genetic disorder and the most common hemoglobin disorder in the United States (U.S.). It affects an estimated 90,000-100,000 Americans and was ranked as the fifth most common principal diagnosis for Medicaid's super-utilizer hospital stays (super-utilizers have 4 or more hospital stays in 1 year) in 2012.⁹ SCD affects vulnerable populations, occurring in 1 in 365 African American births and 1 in 16,305 Hispanic American births in the U.S.¹⁰ Although data reported in 2013 cite an improvement in childhood mortality,¹¹ the median age of death in 2005 was 38 and 42 years for males and females, respectively.¹² These mortality figures are essentially unchanged from data published in the mid-1990s, and result from increased mortality in early adulthood, as youth transition from the pediatric to the adult-oriented health system.^{13, 14} Causes of death include stroke, sepsis, acute chest syndrome, and multi-system organ failure.¹⁴ However, painful vaso-occlusive episodes (VOE) are the most common manifestation of SCD experienced by patients and the most common reason for ED visits.⁷ Severe VOE has been defined as a new onset of pain (7/10 or greater) for at least four hours for which there is no other explanation than vaso-occlusion, requiring treatment with parenteral opioids or with ketorolac.¹ The cause of VOE relates to abnormal red blood cells. Under conditions of stress and de-oxygenation, red cells change shape and are unable to deliver sufficient oxygen to the tissues. This results in tissue ischemia and debilitating pain. Pain from VOE occurs suddenly, is excruciating and unpredictable.¹⁵ VOE often requires treatment in an ED and patients with an increased frequency of VOE have higher morbidity and mortality rates.¹⁶ It is critical that patients with VOE receive evidence-based, timely pain relief. (Of note, VOE was historically referred to as vaso-occlusive crisis (VOC)).

Current Evidence Base for ED Management of VOE: As demonstrated by the recent national survey of emergency physicians (ACEP survey), treatment of VOE is variable and only 12% of ED physicians reported using the National Heart, Lung and Blood Institute (NHLBI) recommendations to treat VOE.⁶ This lack of guideline use may be due in part to the lack of evidence on how to best treat VOE. In one pediatric ED, improvement in pain scores and hospital admission rates were seen over a period of six years after the implementation of pediatric patient-specific analgesic protocols⁴. In a second pediatric ED, the use of a weight-based VOE analgesic protocol and use of intra-nasal fentanyl resulted in improved time to initial and repeat analgesic administration, as well increased number of children being discharged home.⁵ While these findings are encouraging, both projects were conducted in pediatric EDs. Our R34 is the only study directly comparing weight-based and patient-specific analgesic protocols for VOE in adult EDs.²¹ Patient-specific analgesic protocol development and maintenance is labor intensive; high-level evidence will be required to support widespread dissemination.

Patients Perception of ED Treatment of VOE: Given the lack of both a standard of care, or evidenced-based analgesic protocols to treat VOE, it is not surprising that in the ED, SCD patients often report dissatisfaction with care. In a recent cohort study, 81% of patients reported choosing to stay at home to manage their VOE, and of those, 83% reported that past negative ED experience influenced this decision.³ However, patients often require treatment in the ED to not only manage pain but also because other serious complications may exist that require immediate evaluation and treatment.²⁰ ED management of VOE must be evidence-based.

NHLBI Recommendations for ED Management of VOE: NHLBI recognized the need to provide evidence-based recommendations for SCD, including VOE. In September 2014, NHLBI formed an expert panel that published 17 recommendations for treatment of VOE. [name] was an invited member of the panel. None of the recommendations supports the current variability in practice. Only one recommendation (use of opioids) was supported by high-level evidence with a strong recommendation.⁸ The remaining recommendations do not have supporting high-level evidence. A key recommendation was the use of patient-specific analgesic protocols for pain management. When unavailable, a standard VOE analgesic protocol specific for SCD was recommended. However, NHLBI did not define “standard analgesic protocol”. In a 2015 review of the NHLBI recommendations, specific gaps, as well as the need for additional research were identified. The need to conduct research to compare and assess the value of patient-specific and weight-based analgesic protocols for VOE was indicated as a priority research area,² which this Phase III RCT aims to address.

Significance of this Study: Sickle cell disease (SCD) is a chronic disease associated with many medical problems, especially the severe pain referred to as vaso-occlusive episodes (VOE) that leads to an emergency department (ED) visit. We do not know the best way to treat painful VOE in the ED. This phase III randomized clinical trial will identify the best analgesic approach for treating adult SCD patients with VOE during an ED visit. It will determine whether the patient-specific analgesic approach is superior to the weight-based analgesic approach in decreasing the severe pain due to VOE. The trial’s results will shape the health care paradigm for the thousands of SCD patients suffering from severe pain.

4. BASIC STUDY DESIGN

A multi-site Phase III, single blinded, RCT will be conducted to address the study aims. The trial will be conducted at six U.S. sites, with an enrollment period of 24 months. Approximately 460 patients will be consented and randomized in order to obtain the study population of 230 patients with at least one ED visit.

The modified intent to treat (ITT) population is adult SCD patients with an ED visit due to VOE. The primary outcome will be change in pain scores from the time of placement in a treatment area to the time of disposition (hospital admission, discharged home or assigned to observation status) or a maximum treatment duration of 6 hours, whichever

comes first. Due to the logistical difficulty in consenting and randomizing patients during an ED visit due to VOE (see Section 7.2), we plan to screen, consent, and randomize patients in a larger population than the target population of adult SCD subjects with ED visits. There is no reason to think the patients randomized are any different from those who eventually do have an ED visit for VOE. The occurrence of VOE is very unpredictable and not related to overall disease severity. Consented adult SCD patients will be randomized to receive analgesic management for VOE via a weight-based SCD analgesic protocol, or via a patient-specific analgesic protocol developed by their hematologist/sickle cell team, which will be used in the patient's future ED visit due to VOE.

Patients will be told what drug and dose they are receiving during their study ED visit, however, they will remain blinded to which analgesic protocol they are randomized. The primary difference between the two analgesic protocols is the starting opioid dose. Other elements of both analgesic protocols reflect the recommendations in the NHLBI expert panel recommendations document, including recommended route and re-dosing intervals. All analgesic protocols, patient-specific and weight-based, will be written by the SCD provider and uploaded to the electronic medical record (EMR) prior to an ED study visit.

